Appendix 5. Consent and Assent forms	65

Summary

This document describes the protocol for evaluating an intervention to support adolescent girls from marginalised communities in northern Karnataka State, South India to complete secondary school, thereby reducing their vulnerability to HIV infection from early marriage and entry into sex work at young ages.

Overall purpose of the study

The purpose of this study is to evaluate the effectiveness of a multi-part intervention designed to influence adolescent girls (aged around 12-13) from Scheduled Castes and Scheduled Tribes in Northern Karnataka State, India, as well as their families, their schools and the communities in which they live. The intervention aims to improve multi-modal outcomes for these girls, especially the age at which they are married and the age at which they become active in sex work. While there are many pathways that the intervention aims to utilise to achieve these outcomes, the primary pathway is to keep girls in school.

Goal and objectives

The overall goals of the trial: to estimate the effect of a complex structural and behaviour change intervention on the percentage of adolescent girls who enter formal secondary education and the percentage of adolescent girls who complete standard 10. The effect will be estimated by randomizing village communities to either an intervention or a control arm and will use two cohort surveys of adolescent girls to measure the primary outcomes.

Study location

The trial will take place in Bijapur and Bagalkot districts in Northern Karnataka, India.

Study population

The main study population are SC/ST girls who have completed 7th standard, and will be approximately 13 years of age. Girls will be followed-up until they are approximately 16 years of age. Data will also be collected from the girls' parents and schools.

Study design

The study will use a cluster randomized trial design to estimate the effect of the intervention on the proportion of girls married before age 15, as well as other co-primary outcomes. The study will use a cohort of SC/ST girls as the primary data source for estimating effects, with a single endline follow up. Alongside the primary analysis, there will be extensive secondary analyses utilizing data collected in surveys of families and teachers, as well as qualitative data from a variety of stakeholders including boys in the community.

Existing literature on school drop outs and its consequences

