2. Assess the impact of the intervention on age at marriage, age at sexual debut and age of entry into sex work among adolescent SC/ST girls in schools and communities that have access to the intervention.
3. Explore how the intervention has affected the school and the communities' response to premature high school drop-out by SC/ST girls.
4. Investigate the processes and causal pathways through which positive changes occur in the following areas: support and value for education; self-esteem and confidence among adolescent girls; self-perceived safety and social status among adolescent girls and in their social networks; and culturally prescribed social expectations and gender norms.

Study components

This is a rigorous evaluation study that will be implemented by the Karnataka Health Promotion Trust (KHPT), based in Bangalore, Karnataka, in collaboration with the Social and Mathematical Epidemiology Group, London School of Hygiene and Tropical Medicine (LSHTM), and the Centre for

¹⁷ Standards 8, 9, 10.

Global Public Health, University of Manitoba, Canada. The project uses a cluster randomized, controlled trial (RCT) design, and has three main components:

1. A quantitative assessment involving two sequential cohort studies, one initiated in year 1 and another initiated in year 2, of a sample of SC/ST girls and their families at baseline and following the intervention.
2. A qualitative assessment documenting the process of implementation and change using qualitative methods with:
 - a. SC/ST girls
 - b. Families
 - c. Teachers
 - d. Community leaders
 - e. Policy makers
3. A robust monitoring system to monitor the intervention activities at school and community level.

Outcomes

Adolescent girls

This is a complex intervention which aims to act upon many modalities to affect change for SC/ST girls. For that reason we will be collecting a number of outcomes, many of which will be used to understand the effects observed in the primary and the secondary outcomes.

There are four **co-primary outcomes** on which the trial is sized:

1. Proportion of those enumerated in 7th standard (the study cohorts) who ENTER into grade 8th
2. Proportion of those in the study cohorts who complete 10th standard
3. Proportion of girls in the study cohorts who are married at end line.
4. Proportion of girls in the study cohorts who experienced first sexual intercourse at end line

The **secondary outcomes**:

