1. We have reported a range of Risk Ratio minimum detectable effect sizes from 30-40%. This is considered to be the most likely of the outcomes to be influenced by the intervention
2. We have reported a range of Risk Ratio minimum detectable effect sizes from 20-25%. The lower effect size than for outcome 1 reflects the perception that this will be harder to influence with the intervention as the barriers to staying in school increase over time
3. The intervention will target marriage directly through school and home based interventions. Therefore, we aim to decrease the proportion married before 15 by 25-30%.
4. The intervention will target sexual debut directly through school and home based interventions. Therefore, we aim to decrease the proportion married before 15 by 25-30%.

Type 1 error

We have set this at the 5% level

Power

We have set this at the 80% level

Transition from 7-8th Standard

These and further sample size calculations included estimations of variance of between-cluster differences when an unpaired t-test is used for final analysis, on the basis of calculations provided by Hayes and Betnett¹⁹.

Transition from 7-8th standard is considered to be the most likely of the outcomes to be influenced by the intervention, and we have reported a range of minimum detectable effect sizes, with risk ratio of RR= 0.70-0.60.

The detectable effect sizes of RR=0.70-0.60 is assumed on the basis that the intervention aims to bring down the higher dropout rate among SC/ST girls to be in-line with the state average dropout rates among all girls. The *Sarva Shiksha Abhiyan Karnataka Analytical report 2010-11* (Education in Karnataka 2010-11) documents a dropout rate among SC/ST girls during higher primary grades of 9%, compared to 5.6% among all girls in the state (Table 18A). Therefore, the state average for dropout rates from higher primary grades among all girls is 38% less than the dropout rates of SC/ST girls, corresponding to a risk ratio of RR=0.62. Note that the dropout rates of SC/ST girls in transition from standard 7 to standard 8 are not available from the report at district level disaggregates, so we used the state averages for SC girls and all girls. On the basis of this uncertainty, and the event that the intervention is not able to fully bring SC/ST drop out during transition to the average among all girls, we have sized the trial to detect weaker risk ratio of 0.70 under certain, plausible, conditions.

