At project completion, we will assess whether, at follow up, there are significant differences between the intervention and control girls in the key indicators of entering 8th standard, completing tenth standard, being married, having sexual debut and entering into sex work. In the course of the analysis we will present simple cluster summaries for the primary outcomes. We will perform statistical tests, using the t-statistic, to assess the significance of and differences observed between the arms.

The final analysis will assess whether the intervention and control schools, adolescent girls and their families significantly differ in terms of the intermediate and short-term outcomes. As recommended by Hayes and Moulton²², given the large number of clusters and because of reasons related to statistical efficiency, individual-level regression methods will be used to test for significant differences in outcomes between intervention and control arms. For each outcome of interest (e.g., the proportion of girls married at the end of the study period, the proportion of girls passing to 10th Standard, etc.), multivariable logistic regression models using generalized estimating equations (GEE)^{23,24} to address clustering at the school level will be estimated. Stata 11 will be used for all analyses. Similar methods will be used to compare short- and medium-term outcomes among SC/ST girls and their families between intervention and control arms.

Qualitative data analysis

The qualitative data will be transcribed and translated into English. Qualitative analysis packages (eg., NVivo9, ATLAS TI) will be used to identify key issues and themes emerging over time. These findings will be used along with the quantitative findings to understand the impact of the intervention.

Addressing confounding factors, selection bias, spill over effect and impact heterogeneity

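### The primary analysis section adds a fifth, unsized outcome and gives two tests that both reach the co-primary outcomes, with neither named as confirmatory

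*Protocol*

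**What the plan says.** **Outcomes.** The Outcomes section lists four co-primary outcomes and says the trial is sized on them: entry to 8th standard, completion of 10th standard, being married at endline, and, as the fourth, "Proportion of girls in the study cohorts who experienced first sexual intercourse at end line". The Sample size section repeats the same four. The Summary's goals paragraph names only the two schooling outcomes, "the percentage of adolescent girls who enter formal secondary education and the percentage of adolescent girls who complete standard 10", and adds that the design "will use two cohort surveys of adolescent girls to measure the primary outcomes". The Summary's study design paragraph instead refers to "the proportion of girls married before age 15, as well as other co-primary outcomes". The section Analysis of primary outcomes says significance will be assessed at follow-up for entry to 8th standard and for "completing tenth standard, being married, having sexual debut and entering into sex work".

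**Tests.** The first paragraph of that section plans cluster summaries of the primary outcomes, tested with a t-statistic. The sample size text likewise rests on the variance that applies "when an unpaired t-test is used for final analysis". The second paragraph of the analysis section says that "individual-level regression methods will be used to test for significant differences in outcomes between intervention and control arms". It specifies multivariable logistic regression by GEE for each outcome of interest, with clustering at school level.

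**The concern.** An analyst should be able to read from the protocol which outcomes carry the primary claim and which p-value decides each of them. Neither is settled here.

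The fifth indicator sits under a heading about primary outcomes but has no place in the outcome hierarchy. A favourable result on entry into sex work could be reported as primary, and an unfavourable one set aside as unlisted. The text supports either course.

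For the four listed outcomes, the t-test and the GEE model can give different answers. They differ in the unit of clustering (the village was randomised, whereas the GEE clusters on school), in adjustment (unadjusted summaries against a multivariable model) and in effect measure (cluster summaries against odds ratios). With neither named as decisive, the choice can be made after both are seen.

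**Working it through.** **1. Which test the sizing uses.** Inputs from the Sample size section, retention table: control proportion p0 = 0.30, intervention proportion p1 = 0.231 (23% reduction), m = 28 girls per cluster, k = 0.15, 0.20 and 0.25, type 1 error 5%, power 80%. The protocol does not state sidedness; two-sided is assumed because it reproduces the tables. The formula for unmatched clusters analysed by an unpaired t-test is

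c = 1 + (1.96 + 0.84)² × [p0(1−p0)/m + p1(1−p1)/m + k²(p0² + p1²)] / (p0 − p1)²

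For k = 0.20, with unrounded normal quantiles so that the squared term is 7.849:
- p0(1−p0)/m = 0.21/28 = 0.00750
- p1(1−p1)/m = 0.1776/28 = 0.00634
- k²(p0² + p1²) = 0.04 × 0.1434 = 0.00573
- sum = 0.01958; (p0 − p1)² = 0.004761
- c = 1 + 7.849 × 0.01958/0.004761 = 33.3

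The three values of k give 29.1, 33.3 and 38.6, exactly as printed. The transition and marriage tables reproduce in the same way. (In the sexual intercourse table the rows with a 30% control proportion do not reproduce from their printed inputs. That is a separate matter and does not bear on this point.) The trial is therefore sized on the cluster-level t-test, with each outcome at the full 5%.

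**2. Which outcomes are sized.** The control proportions, the risk ratios and the four sets of tables all cover the same four outcomes. There is no control rate, effect or cluster count for entry into sex work.

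**3. Where entry into sex work appears.**
- Summary, overall purpose: named, as the age at which girls become active in sex work.
- Study questions: part of question 2.
- Table 4: measured, under impact and long-term outcomes.
- Co-primary list: absent.
- Secondary list: absent.
- Analysis of primary outcomes: present, among the indicators to be tested.

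It is a declared and measured outcome without a rank.

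**4. Whether GEE reaches the co-primary outcomes.** The GEE paragraph opens with outcomes of the intermediate and short-term kind. Its first worked example, however, is marriage at the end of the study, which is co-primary outcome 3, and its second concerns progress to 10th standard. Its last sentence then extends the same approach to short- and medium-term outcomes in girls and families. That would be redundant if the paragraph had dealt only with such outcomes. So the GEE model covers co-primary outcomes as well.

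**5. Count.** Four co-primary outcomes × two tests = eight admissible p-values where there should be four. If entry into sex work is counted as primary, 5 × 2 = 10.

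**The case against.** **The primary set is explicit.** The four outcomes are numbered, labelled co-primary and repeated in the sizing. This stands. A reader might infer that the protocol holds three rival primary sets, of two, four and five outcomes. The text does not support that. The two come from a goals sentence, and the same Summary goes on to speak of marriage and other co-primary outcomes. The five are called key indicators, not primary outcomes. The goals sentence is incomplete and the analysis sentence adds an item; neither is a competing list.

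**Entry into sex work is not hidden.** This also stands. It is part of the purpose, the study questions and Table 4. The defect is its missing rank and its position under a heading on primary outcomes.

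**The t-test could be meant for the primary outcomes and GEE for the rest.** The opening words of the GEE paragraph favour this reading, but the marriage example and the closing sentence defeat it. An ambiguity remains that only the authors can remove.

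**The analysis plan may name the confirmatory test.** It may. But the protocol is not silent on the point: it states two tests for the same outcomes, and an analysis plan written from it inherits the conflict.

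**GEE has a stated rationale.** The protocol cites the large number of clusters and statistical efficiency. That is a reason to run the model. It does not say which result decides.

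**Conclusion.** The point holds in limited form. The four co-primary outcomes are clear. What is not fixed is the standing of a fifth, unsized outcome tested under the primary heading, and which of two tests decides each co-primary outcome. That leaves eight admissible p-values for four outcomes, or ten if the fifth is counted.

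A reader might go further and quote a false-positive risk of 22.6% for five outcomes (1 − 0.95⁵) against 18.5% for four (1 − 0.95⁴). Those figures hold only if the outcomes are independent, each is tested at 5%, and success on any one is enough. The protocol states no success rule, and marriage and sexual debut are plausibly positively related, which would lower both figures. Even on those assumptions the fifth outcome adds only about 4 points. The conclusion does not rest on these figures; it rests on the conflicting text and on the reproduced sizing, which shows that the t-test is the test the cluster numbers assume.

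**What to change.** 1. In Analysis of primary outcomes, limit the sentence on significance testing to the four co-primary outcomes of the Outcomes section.
2. Add entry into sex work to the secondary list. With no control rate, effect or cluster count, it has no basis as a primary outcome.
3. Align the goals sentence in the Summary with the four outcomes.
4. Name one confirmatory test for the co-primary outcomes and call the other supportive. The village-level t-test on cluster summaries is the consistent choice, since the trial is sized on it and villages were randomised. If the sponsor prefers GEE for efficiency, the sizing text and the level of clustering must be brought into line with it.
5. Reword the GEE paragraph so that its opening, examples and last sentence agree on which outcomes it covers.

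The cost is protocol wording only. Data collection, recruitment and the number of villages are unchanged.

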The study will employ a cluster randomized design. A cluster randomized design was chosen because the intervention is at a cluster level, i.e. many components of the intervention will not be delivered to specific individuals but to the schools and the communities where the individuals study and reside.

Site selection and cluster definition

The village is the unit of randomization. The village was chosen as the unit of randomization instead of the school so as to minimize the contamination between schools in the same village. In addition, some aspects of the intervention will act at the community level. In this setting, villages are sufficiently isolated so as to minimize contamination between villages.

Sampling of the adolescent girls

The project indicators for the SC/ST adolescent girls listed will be measured through two sequential cohort studies. Each SC/ST girl in the intervention and control clusters were profiled, This involved administering a brief questionnaire by trained outreach staff to the family of every listed SC/ST girl in

the study villages (control and intervention arms) to ascertain the girl's age, religion, family background and if they completed 7th standard. This information was used to help validate the denominator (ascertained through earlier mapping exercises) and to provide accurate data on the number of SC/ST girls attending and completing 7th standard school (the register lists provided by schools on SC/ST girls enrolled is frequently inflated). Girls will be invited to join the study at the end of 7th standard in year 1 (cohort 1) and year 2 (cohort 2), and each girl will be followed up until the start of year 4. By this point, most or all of the girls in both cohorts will have reached 15 years of age. By having two cohorts we can increase the available sample size and allow for the possibility that some of the intervention components will be more effective as they become established.

Sampling

Bijapur and Bagalkot district were pre-selected based on the high proportion of SC/ST girls in these districts, the programme rollout possibilities, existing infrastructure and rapport with the communities in these districts.

Enumeration of high schools

A high school enumeration was carried out by the existing project staff in these two districts. A standard format was developed to collect the information from these high schools with the following objectives;

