The *District Level Household Surveys (DLHS-2007-08)* collected data on age at marriage and has a reasonable sample size in each district. About 21% of the women aged 18-25 married before the age of 15 years. A higher percent of SC/ST women were married as compared to others (25.9% against 19.3%). Therefore, bringing the proportion in-line with all girls would result in a risk ratio of 0.75.

1-type I	Power	Control p	Cluster Size	% reduction	Intervention p	K	# clusters per arm		
0.95	0.80	35%	28	25%	26.3%	0.15	20.8		
						0.20	24.3		
						0.25	28.7		
		28	30%	24.5%	0.15	14.4			
					0.20	16.7			
					0.25	19.6			
		0.95	0.80	30%	28	25%	22.5%	0.15	24.6
								0.20	28.0
								0.25	32.4
28	30%			21.0%	0.15	16.9			
					0.20	19.2			
					0.25	22.1			
0.95	0.80			20%	28	25%	15.0%	0.15	37.7
								0.20	41.1
								0.25	45.5
		28	30%	14.0%	0.15	25.8			
					0.20	28.0			
					0.25	31.0			

Proportion having had sexual intercourse before age 15

[figure not shown]
The intervention will target sexual debut directly through school and home based interventions. Therefore, we aim to decrease the proportion married before 15 by 25-30%. This is assumed to be equal to the previous indicator i.e. proportion married.

1-type I	Power	Control p	Cluster Size	% reduction	Intervention p	K	# clusters per arm		
0.95	0.80	35%	28	25%	26.25%	0.15	20.8		
						0.20	24.3		
						0.25	28.7		
		28	30%	24.50%	0.15	14.4			
					0.20	16.7			
					0.25	19.6			
		0.95	0.80	30%	28	25%	22.50%	0.15	34.1
								0.20	37.5
								0.25	41.9

				30%	21.00%	0.15	23.4
						0.20	25.6
						0.25	28.5
0.95	0.80	20%	28	25%	15.00%	0.15	37.7
						0.20	41.1
						0.25	45.5
				30%	14.00%	0.15	25.8
						0.20	28.0
						0.25	31.0

K and the number of clusters

[figure not shown]
We are uncertain about the value of k – the between school variation in the outcomes – and therefore explored the relationship between the number of clusters and the value of K for some central and realistic estimates of the above parameters. The relationship is shown for three different effect sizes: 30%, 33%, 35% for the effect on transition from 7-8th standard, and 20%, 23%, 25% for the retention until 10th standard. The power is 80%, type 1 is 5%, number of girls per cluster is 14 (accounting for loss to follow-up), and the proportion in the controls is 13% and 30% for transition and retention, respectively. We have included 34 clusters per arm as the reference line.

[figure not shown]

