After allocating the villages to intervention and control arms, there were 12 villages where there was a possibility of contamination because these villages were contiguous with a village in a different arm of the study. To compensate for potential loss of statistical power due to contamination we therefore selected an additional 12 villages (6 intervention and 6 control arm) for inclusion in the study as follows: Of the 53 villages remaining in the sampling frame, we excluded 24 due to their close proximity to villages which had already been selected for the study. From the remaining 29 villages in the sampling frame, an additional 12 villages (6 intervention arm and 6 control arm) with 19 high schools (9 intervention arm and 10 control arm) were randomly selected to be included in the study.

Thus a total of 80 villages (40 in each arm) with 144 high schools (71 intervention arm and 73 control arm) will be included in the study (see diagram below).

Summary diagram

Data collection

In each of the intervention and control villages, quantitative and qualitative assessments will be carried out, both at baseline and following the intervention, among the target groups listed in Table 1.

Closed-ended questionnaires (used in the sequential cohort studies among adolescent girls and their families) have been developed based on a review of available measurement tools. Questionnaires are in Appendix 2. All instruments will initially be developed in English, translated into *Kannada* (the local language), pretested and piloted and revised, and then back-translated. Tables 4, 5 and 6 provide summaries of the different major domains and sub-domains under each indicator that will be measured in these sequential cohort surveys among the adolescent girls and their parents, respectively.

Table 4: Indicator domains and sub-domains that will be measured in sequential cohort studies of SC/ST adolescent girls in control and intervention villages, using a structured behavioural questionnaire

Major domains	Minor domains
Impact and long-term outcomes	
Demographics	Geographic location, school, age, caste, age at menarche, number of siblings in the family (male and female), parents' living status, their education, occupation, land holdings and household income, whether anyone in the family is a Devadasi/sex worker, and relationship to the adolescent girl

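### The GEE clusters by school although villages were randomised, so its 5% level is exceeded if schools in one village are correlated

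*Protocol*

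**What the plan says.** Under site selection and cluster definition, the Protocol states: "The village is the unit of randomization". Villages were preferred to schools "so as to minimize the contamination between schools in the same village", and because parts of the intervention act on the community. The section on contamination gives the final count: "Thus a total of 80 villages (40 in each arm) with 144 high schools", 71 in the intervention arm and 73 in the control arm. All schools in a village are therefore in the same arm.

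The section on analysis of primary outcomes plans two analyses. The first presents cluster summaries for the primary outcomes, with this test: "We will perform statistical tests, using the t-statistic, to assess the significance of and differences observed between the arms". The second says that "individual-level regression methods will be used to test for significant differences in outcomes between intervention and control arms", and specifies multivariable logistic GEE models for each outcome of interest "to address clustering at the school level will be estimated". Its examples are the proportion married and the proportion passing to 10th standard.

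The sample size is derived for the case "when an unpaired t-test is used for final analysis". The section on k and the number of clusters describes k as "the between school variation in the outcomes", and the allocation section speaks of schools being allocated just before it describes the randomisation of villages.

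**The concern.** The robust variance of a GEE is valid when the clusters it sums over are independent, so they must be at or above the unit of randomisation. Here they sit one level below it. Girls in two schools of one village share the allocation, the community-level intervention and the local norms on marriage and schooling that the protocol names as drivers of the outcomes. The protocol's own reason for randomising villages is that such schools influence each other.

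Clustering by school leaves the covariance between schools in a village out of the variance of the treatment effect. If that covariance is positive, standard errors are too small, confidence intervals too narrow, and the test rejects a true null more often than 5%. The GEE covers co-primary outcomes and is described as testing for differences between arms, so it could be the analysis on which the trial's conclusions rest.

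**Working it through.** **Inputs from the Protocol.** 80 villages and 144 schools, so 144/80 = 1.8 schools per village. Girls per village: 1050/40 = 26.25 enrolled, or 28 in the sample size tables. Control proportions p in the tables run from 9% to 40%, and k is 0.15, 0.20 or 0.25. Alpha is 5%, taken as two-sided.

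**Reproducing the plan's own figure.** For marriage at 30% control risk, 25% reduction, m = 28, k = 0.25:

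c = 1 + (1.96 + 0.84)² × [p0(1−p0)/m + p1(1−p1)/m + k²(p0² + p1²)] / (p0 − p1)²

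= 1 + 7.85 × [0.00750 + 0.00623 + 0.00879] / 0.075² = 32.4 clusters per arm, as tabulated. So k is read correctly, and a cluster of 28 girls is set against 40 villages per arm.

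**Formula for the error rate.** Let ρ = k²p/(1−p), let m be girls per village, ms = m/1.8 girls per school, and f the share of ρ at village level.

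- Design effect seen by the school-clustered GEE: DS = 1 + (ms − 1)ρ
- True design effect: DT = DS + (m − ms)fρ
- Type I error = 2[1 − Φ(1.96 √(DS/DT))]

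**Worked example**, p = 0.30, k = 0.25, m = 26.25:

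- ρ = 0.0625 × 0.30/0.70 = 0.0268; ms = 14.58; DS = 1 + 13.58 × 0.0268 = 1.364
- f = 1: DT = 1.364 + 11.67 × 0.0268 = 1.676; standard error 9.8% too small; type I error 7.7%
- f = 0.5: DT = 1.520; standard error 5.3% too small; type I error 6.3%
- f = 0: DT = DS; type I error 5.0%

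**Ends of the range:**

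| p, k, m | All at village level | Half | None |
|---|---|---|---|
| 0.09, 0.15, 26.25 | 5.3% | 5.1% | 5.0% |
| 0.30, 0.25, 26.25 | 7.7% | 6.3% | 5.0% |
| 0.40, 0.25, 28 | 8.8% (DT 2.125, DS 1.606) | 6.9% (DT 1.866) | 5.0% |

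Over this range the standard error is 1% to 13% too small if all variation is at village level, and 1% to 7% too small if half is.

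**Simulation under the null**, with 71 + 73 schools in 40 + 40 villages, 1 to 4 schools per village, 26 girls per village and 8,000 runs (Monte Carlo standard error about 0.25 points). Both GEEs used an independence working correlation, a K/(K−1) correction (K = number of clusters) and a t reference, so the difference between them is due to the level of clustering:

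| p, k, share at village level | School GEE | Village GEE | Village t-test |
|---|---|---|---|
| 0.30, 0.25, all | 7.2% | 5.0% | 5.1% |
| 0.30, 0.25, half | 5.8% | 4.9% | 4.8% |
| 0.40, 0.25, all | 7.6% | 4.9% | 5.0% |
| 0.40, 0.25, half | 6.5% | 5.1% | 5.2% |

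At p = 0.13, k = 0.20 the school GEE gave 5.1% to 5.3%, within simulation error of 5%.

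**Sensitivity to village size.** Further runs (6,000 each, normal reference, all variation at village level) varied how schools and girls are spread over villages. At p = 0.30, k = 0.25 the school GEE gave 6.8% to 10.2%, the village GEE 5.3% to 6.2% and the village t-test 4.7% to 5.2%. The highest rate was 12.1%, at p = 0.40, k = 0.25, with 15 girls per school and an uneven number of schools per village; the village GEE gave 6.2% there.

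**The case against.** - **The primary outcomes already have a valid test.** The t-test on cluster summaries is planned for them, the trial was sized on it, and the cluster is defined earlier as the village. This stands: on village summaries that test holds its level. It does not correct the GEE, which the same section applies to each outcome of interest. The paragraph containing the GEE does open with intermediate and short-term outcomes, but its first example is marriage.
- **School may be loose wording for cluster.** This is possible, since the text mixes the two units elsewhere. But an analyst following the section as written would cluster by school.
- **The closed form overstates the error.** It treats every village as having 1.8 equal schools. With equal girls per village, single-school villages carry no error: for p = 0.40, k = 0.25, m = 28, the tightest spread (8 villages with one school and 32 with two, per arm) gives 8.3% in place of 8.8%. If instead girls are proportional to schools, the rate goes up, as the sensitivity runs show. So 8.8% is not an upper bound in either direction of argument.
- **Key inputs are missing.** The village/school split and the spread of schools are not given. Moreover, girls enrol at the end of 7th standard, whereas the 144 are high schools, so a girl who never enters 8th has no high school to be clustered in. This weakens the figures but not the mismatch of units.
- **Some remedies belong in an analysis plan.** Naming the deciding test and adding a small-sample correction are commonly left there. Agreed; the point does not depend on them.

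**Conclusion.** The concern holds. The protocol fixes the GEE at a level below the randomised unit, and this can only be harmless if schools in one village are uncorrelated, which its own rationale for randomising villages argues against. On its own p and k, with 1.8 schools per village, the nominal 5% becomes 5.3% to 8.8% if all variation is at village level and 5.1% to 6.9% if half is; uneven villages can push it higher. The excess is negligible for outcomes with a low control proportion, such as transition to 8th standard, and largest for retention, where the tables go up to 40%. The figures assume a two-sided test and k as variation between villages; the split of that variation is an assumption.

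**What to change.** In the section on analysis of primary outcomes, specify that the GEE clusters by village (80 villages, the unit of randomisation) in place of school. That one change corrects the analysis, and it remains valid even if schools in a village turn out to be uncorrelated.

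Three additions would help but are secondary:

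- State that the t-test uses village summaries, and which of the two tests decides for each co-primary outcome; preferably give the village GEE a small-sample correction.
- Analyse each girl in her village at enumeration. The text already keeps girls who transfer outside the trial in their arm.
- Use village in place of school in the definition of k and in the allocation section.

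The cost is a few words and one sentence, with no change to design or data collection. GEE intervals become wider: in the closed form, by nothing if there is no village-level correlation, and by √(2.125/1.606) = 1.15, or 15%, at p = 0.40, k = 0.25 with all variation at village level. That extra width is the uncertainty which school-level clustering leaves out.
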